3 INVESTIGATIONAL PLAN

3.1 Study Design and Duration

Study Design: This is an exploratory, open-label, multicenter study of nivolumab and nivolumab in combination with ipilimumab.

Approximately 150 subjects with advanced melanoma (unresectable or metastatic) will be treated in this study in four (4) parts. Part 1 of this study will have two (2) cohorts consisting of approximately 40 patients each: cohort 1 will consist of anti-CTLA4 therapy-naïve patients and cohort 2 will consist of patients who have progressed on an anti-CTLA-4 regimen. Cohorts 1 and 2 will be administered nivolumab at 3 mg/kg dose level every 2 weeks. Subjects will go through a **screening period** of no longer than 28 days and eligible subjects will start the **treatment period** for a duration of 2 years depending on their response. Nivolumab will be administered by IV infusion every 14 days in 56 day cycles (on days 1, 15, 29 and 43 of each cycle). Response assessments will be performed on days 49-56. The response assessment must be completed before the first dose in the next cycle.

In Part 2, approximately 20 anti-CTLA4 therapy-naïve patients will be administered nivolumab at 1 mg/kg and ipilimumab at 3 mg/kg every 3 weeks for 4 doses, followed by nivolumab 3 mg/kg alone every 2 weeks (Arm A). This part of the study is aimed at defining the optimal window for on-treatment biopsy with concurrent nivolumab and ipilimumab therapy. All subjects will be required to undergo a pre-treatment biopsy and consent to on-treatment biopsy. Two (2) groups of approximately 10 patients each will be enrolled sequentially with the first group assigned to an on-treatment biopsy between Days 8 and 15 (weeks 2 and 3) after the start of therapy and the second group assigned to an on-treatment biopsy between Days 22 and 29 (subsequent to the second dose of therapy between weeks 4 and 5) after the start of therapy. Optimal biopsy timing will be defined as the biopsy window with the greatest pharmacodynamic

increase in intratumoral activated T cells compared to the pre-treatment biopsy. The defined optimal on-treatment biopsy window will be used in the third part of this study.

In Part 3, approximately 30 anti-CTLA4 therapy-naive patients will be randomized 2:1 and treated with one of the following:

- Arm A: nivolumab 1 mg/kg IV combined with ipilimumab 3 mg/kg IV Q3W for 4 doses then nivolumab 3 mg/kg IV Q2W
- Arm B: nivolumab 3 mg/kg IV Q2W

In Part 4, approximately 20 anti-CTLA4 therapy-naive patients with brain metastases will be randomized 1:1 and treated with one of the following:

- Arm D: nivolumab 1 mg/kg IV combined with ipilimumab 3 mg/kg IV Q3W for 4 doses then nivolumab 3 mg/kg IV Q2W
- Arm E: nivolumab 3 mg/kg IV Q2W

In Parts 2, 3 and 4 of this study, patients will also go through a screening period of no longer than 28 days. In Parts 2 and 3, pre-treatment samples will be centrally assessed for tumor content and subjects who have samples with insufficient tumor content (≤ 100 tumor cells in a 4 micron tissue section) will require re-biopsy or will not be treated. In Part 4, tumor biopsy collection is optional, but strongly encouraged if clinically safe. Eligible subjects will then start the treatment period for a maximum of two years of therapy. Subjects randomized to Arm C in Part 3 of this study prior to the closure of this Arm have the option to receive nivolumab monotherapy upon consultation with the medical monitor.

Response assessments will be performed approximately every 8 weeks (may differ by several weeks depending on treatment arm). The response assessment must be completed before the first dose in the next treatment visit.

A study schema is presented below in [Figure 3.1](#).

[figure not shown]
At the completion of 2 years of therapy, those subjects who are benefiting and still meet study criteria may continue after discussion and agreement between the investigator and Medical Monitor and will enter the Extension Period (See [Section 4.3.7](#)). Treatment in the Extension Period will continue until progression of disease or unacceptable toxicity.

Subsequent to a duration of 2 years of active treatment or following the last dose of treatment in the Extension Period, each patient will continue **follow-up** consisting of office visits, lab work and tumor assessments for a maximum period of up to 100 days; follow-up office visits 1 and 2 (40-60 days and 101-120 days after the stop of study therapy). Completion of subsequent follow-up office visits will depend on the status of the subject at the end of the treatment period.

Patients with confirmed disease progression as described in [Sections 1.1.9](#) and [4.3.8](#) will complete follow-up office visits 1 and 2 and will then continue follow-up by **telephone assessment** every 3 months for the remainder of time left to complete 2 years from the first dose of treatment.

All patients will be followed for overall survival assessment by telephone contact every 3 months from the last follow-up office visit for the remainder of time left to complete 2 years from the first dose of therapy. Patients that enter the Extension Period will be followed for overall survival assessments up to a maximum of 100 days after the last treatment dose.

Figure 3.1: Study schema

* At the completion of two years of therapy, those subjects who are benefiting and meet criteria may continue after discussion and agreement between the Investigator and Medical Monitor and will enter the Extension Period (See Section 4.3.7).

Subjects may be treated beyond PD, refer to Section 4.3.8*In Parts 3 and 4:

- nivolumab (3 mg/kg) as monotherapy will be infused over 30 minutes
- for the combination, nivolumab (1 mg/kg) will be infused over 30 minutes and after a 30-minute break, ipilimumab (3 mg/kg) will be infused over 30 minutes, then nivolumab (3mg/kg) will be infused over 30 minutes

Number of Subjects: approximately 150 subjects treated

Duration of Study: The study is expected to accrue over a period of approximately 2 years.

- maximum 28 days of screening
- At the completion of 2 years of therapy, those subjects who are benefiting and still meet study criteria may continue after discussion and agreement between the investigator and Medical Monitor and will enter the Extension Period (See Section 4.3.7)
- approximately 3 months follow-up office visits (including tumor assessments)

- 2 year overall survival assessment (by telephone contact) from first therapy dose for time remaining from last follow up office visit or for those patients that enter the Extension Period, overall survival assessments will be continued for 100 days following the last treatment dose.

3.2 Post Study Access to Therapy

Not applicable for this study

3.3 Study Population

Eligibility criteria for this study have been carefully considered to ensure the safety of the study subjects and to ensure that the results of the study can be used. It is imperative that subjects fully meet all eligibility criteria. No exceptions will be granted.

For entry into the study, the following criteria MUST be met.

3.3.1 Inclusion Criteria

1) Informed Consent:

- a) Signed, written Informed Consent must be obtained prior to the performance of any study related procedures that are not considered part of standard of care

2) Target Population:

- a) Subjects with advanced melanoma (unresectable or metastatic) who have received and either progressed or discontinued on no more than 3 prior treatment regimens or have refused standard therapy for treatment of metastatic melanoma.
 - i. Subjects may have been treated or offered treatments for melanoma (e.g., chemotherapy, biological therapy, targeted therapy, vaccine therapy or cytokine therapy).
 - ii. Subjects who have never received any treatment for metastatic disease, ie. newly diagnosed subjects, may be allowed on study if they have been offered and have refused standard therapy or are deemed to be inappropriate candidates for standard therapy by the investigator.
 - iii. Subjects enrolled to Cohort 1 and Arms A, B, D and E (see [Figure 3.1](#)) must never have received anti-CTLA4 therapy (anti-CTLA4 naive).
 - iv. Subjects enrolled to cohort 2 (see [Figure 3.1](#)) must have had anti-CTLA4 monoclonal antibody (mAb) based therapy as 1 of the prior regimens (anti-CTLA4 progressors). If anti-CTLA4 mAb therapy was the last treatment regimen prior to study entry, the last dose of anti-CLTA4 mAb must have been administered at least 6 weeks prior to initiation of study therapy. Relapse during or within 6 month of last dose of anti-CTLA4 mAb adjuvant treatment for completely resected melanoma alone will also fulfill this criterion.
 - v. Subjects enrolled to Arms D and E
 - (1) Must have at least one measurable index brain metastases > 0.5 cm and not larger than 3 cm that has not been previously irradiated

- (2) Index brain lesions must not have sequela of prior therapy that would confound attribution of tumor response including edema or hemorrhage
 - (3) Must not have neurologic symptoms secondary to metastatic lesions
 - (4) Must not have received systemic corticosteroids within 14 days prior to initiation of study therapy.
- b) Subjects must have histologic confirmation of advanced melanoma. Confirmation of diagnosis must be obtained from the pre-treatment biopsy if it is not available from a prior diagnostic procedure.
- c) Subjects must consent to allow the acquisition of existing (archival) formalin-fixed paraffin-embedded (FFPE) material (block or a minimum of 10 unstained slides) for performance of correlative studies.
- d) Subjects must have at least one measurable lesion at baseline by CT or MRI as per RECIST 1.1 criteria (see [Appendix 2](#)).
- i. Tumor sites used to satisfy this criterion must not have received any prior radiation therapy.
 - ii. Sites for biopsy must be distinct from target lesions used for efficacy assessment.
- e) Subjects must have at least 1 tumor site that can be biopsied at acceptable clinical risk, as judged by the Investigator, and must consent to pre-treatment and on-treatment tumor biopsies. For Part 4, pre-treatment and on-treatment biopsies are optional, but strongly encouraged.
- i. Lesions should not have received prior radiation therapy
 - ii. These sites must be designated for biopsy prior to the first treatment, to avoid selection bias that may affect study endpoints.
 - iii. In Part 1, pathologic confirmation of viable tumor cells (touch imprint cytopathology) from collected tissue samples is strongly recommended to permit consideration of repeat biopsy if deemed of acceptable clinical risk. Subjects for whom pre-treatment adequate tissue biopsy (demonstration of tumor cells on touch prep) cannot be achieved may still remain on study and continue to receive study therapy and undergo other sample collections. However, that subject will then be replaced.
 - iv. In Parts 2 and 3, pre-treatment tumor samples must contain sufficient tumor content (≤ 100 tumor cells/4-micron tissue section) upon central assessment. If sample contains insufficient tumor content, a re-biopsy will be required to obtain a sample with sufficient tumor content prior to treatment.
 - v. The site of biopsy should not include lymph nodes in Parts 2, 3 and 4.
- f) Subjects must have ECOG performance status ≤ 1 (See [Appendix 1](#)).
- g) Subjects must have the ability to comply with treatment, PK, biomarker sample collection, and required study follow-up.
- h) Organ and marrow function as follows (blood product transfusion is not permitted in the 4 weeks prior to achieve entry criteria):
- i. White blood cell count $\geq 2,000$ cells/mm³

- ii. Neutrophils $\geq 1500/\mu\text{L}$ (stable, off any growth factor for at least 4 weeks prior to study drug administration)
 - iii. Platelet count $\geq 100,000/\text{mm}^3$
 - iv. Hemoglobin $\geq 9.0 \text{ g/dL}$
 - v. Total bilirubin $\leq 1.5\text{x}$ the institutional upper limit of normal (IULN)
 - vi. Subjects with Gilbert's syndrome are eligible if their total bilirubin is less than 3.0 mg/dl
 - vii. ALT (alanine aminotransferase) and AST (aspartate aminotransferase) $\leq 3\text{x}$ IULN
 - viii. Estimated GFR (eGFR) calculated via MDRD or Cockcroft-Gault equations $\geq 40 \text{ mL/min}$
- i) Known BRAF V600 mutation status (Parts 2, 3 and 4). Subjects with either V600 wild-type or V600 mutation-positive status, are eligible.

3) Age and Reproductive Status:

- a) Males and females ≥ 16 years of age.
- b) Women of childbearing potential:
 - i. Women of childbearing potential (WOCBP) must use method(s) of contraception based on the tables in [Appendix 3](#). A highly effective method(s) of contraception (failure rate of less than 1% per year) is required. The individual methods of contraception should be determined in consultation with the investigator. WOCBP must follow instructions for birth control when the half life of the investigational drug is greater than 24 hours, contraception should be continued for a period of 30 days plus the time required for the investigational drug to undergo five half lives (total of 23 weeks after the last dose of investigational product).
 - ii. Women must have a negative serum or urine pregnancy test (minimum sensitivity 25 IU/L or equivalent units of HCG) within 24 hours prior to the start of investigational product.
 - iii. Women must not be breastfeeding.
- c) Men who are sexually active with WOCBP must use any contraceptive method with a failure rate of less than 1% per year. Men that are sexually active with WOCBP must follow instructions for birth control when the half life of the investigational drug is greater than 24 hours, contraception should be continued for a period of 90 days plus the time required for the investigational drug to undergo five half lives (total of 31 weeks after the last dose of investigational product).
- d) Women who are not of childbearing potential (ie, who are postmenopausal or surgically sterile; see [Section 3.3.3](#) for the definition of WOCBP) and azoospermic men do not require contraception.

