- Arm D: nivolumab 1 mg/kg IV combined with ipilimumab 3 mg/kg IV Q3W for 4 doses then nivolumab 3 mg/kg IV Q2W
- Arm E: nivolumab 3 mg/kg IV Q2W

In Parts 2, 3 and 4 of this study, patients will also go through a screening period of no longer than 28 days. In Parts 2 and 3, pre-treatment samples will be centrally assessed for tumor content and subjects who have samples with insufficient tumor content (≤ 100 tumor cells in a 4 micron tissue section) will require re-biopsy or will not be treated. In Part 4, tumor biopsy collection is optional, but strongly encouraged, if clinically safe. Eligible subjects will then start the treatment period for a duration of two years of therapy. Subjects randomized to Arm C in Part 3 of this study prior to the closure of this Arm have the option to receive nivolumab monotherapy upon consultation with the medical monitor. Response assessments will be performed approximately every 8 weeks (may differ by several weeks depending on treatment arm). The response assessment must be completed before the first dose in the next treatment visit.

[figure not shown]
A study schema is presented below in [Figure 1](#).

At the completion of 2 years of therapy, those subjects who are benefiting and still meet study criteria may continue after discussion and agreement between the investigator and Medical Monitor and will enter the Extension Period (See [Section 4.3.7](#)).

Subsequent to a duration of 2 years of active treatment or following the last dose of treatment in the Extension Period, each patient will continue follow-up consisting of office visits, lab work and tumor assessments for a maximum period of up to 100 days; follow-up office visits 1 and 2 (40-60 days and 101-120 days after the stop of study therapy). Completion of subsequent follow-up office visits will depend on the status of the subject at the end of the treatment period.

All patients who have not completed 2 years of treatment will be followed for overall survival assessment by telephone contact every 3 months from the last follow-up office visit for the remainder of time left to complete 2 years from the first dose of treatment. Patients that enter the Extension Period will be followed for overall survival assessments up to a maximum of 100 days after the last treatment dose.

Figure 1: Study Schema

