* At the completion of two years of therapy, those subjects who are benefiting and meet criteria may continue after discussion and agreement between the Investigator and Medical Monitor and will enter the Extension Period (See Section 4.3.7).

**Subjects may be treated beyond PD, refer to Section 4.3.8

***In Parts 3 and 4, infusion times for nivolumab and ipilimumab will be as follows:

- nivolumab (3 mg/kg) monotherapy will be infused over 30 minutes
- for the combination, nivolumab (1 mg/kg) will be infused over 30 minutes and after a 30-minute break, ipilimumab (3 mg/kg) will be infused over 30 minutes, then nivolumab (3 mg/kg) will be infused over 30 minutes

Duration of Study: The study is expected to accrue over a period of approximately 2 years.

- maximum 28 days of screening

- At the completion of 2 years of therapy, those subjects who are benefiting and still meet study criteria may continue after discussion and agreement between the investigator and Medical Monitor and will enter the Extension Period (See Section 4.3.7).
- approximately 3 months follow-up office visits (including tumor assessments)
- 2 year overall survival assessment (by telephone contact) from first therapy dose for time remaining from the last follow up office visit or for those patients that enter the Extension Period, overall survival assessments will be continued for 100 days following the last treatment dose.

Number of Subjects: approximately 150 subjects will be treated

Estimated Enrollment: approximately 200 subjects will be screened (25% screen fail rate)

Study Population: The study population will include men and women age 16 or older with a histological diagnosis of advanced melanoma (unresectable or metastatic). All subjects must have measurable disease. Subjects must also have accessible tumor that can be biopsied at acceptable clinical risk (as judged by the investigator, with the exception of subjects with brain metastases enrolled in Arms D and E) and must consent to pre-treatment and on-treatment tumor biopsies. Tumor biopsy sites must be distinct from evaluable lesions and not have been irradiated prior to entry. Cohort 1 and Arms A, B, D and E will consist of subjects who are anti-CTLA-4 therapy naive and cohort 2 will consist of subjects who have progressed on anti-CTLA-4 therapy.

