5 STUDY ASSESSMENTS AND PROCEDURES

5.1 Flow Chart/Time and Events Schedule

Table 5.1A: CA209038 Screening Procedural Outline			
Procedure	Screening Visit	Visit 1 Day -3 to Day 1	Notes
Eligibility Assessments			
Informed Consent	X		A subject is considered enrolled only when a protocol-specific informed consent is signed
Inclusion/Exclusion Criteria	X		All inclusion/exclusion criteria should be assessed prior to study assignment
Medical History	X		Include all previous treatments, any toxicities or allergy related to previous treatments, history of tobacco use (how many packs for how many years) and other pulmonary history (e.g. asthma or toxic exposures)
BRAF mutation status	X		A hard copy of BRAF mutation status must be made available to the investigator and the Sponsor. For Part 1 only: If BRAF status is not known, then subjects' archival tumor tissue will be sent for centralized testing at a Sponsor-selected lab. Fresh tumor tissue should be used for BRAF mutation status only if the BRAF status is unknown, no archival tumor tissue is available and if there is adequate tumor tissue for all other tumor tissue assays.
Tumor tissue samples	X		For Part 1, must have lesions from which a minimum of 2 core biopsies for FFPE and RNA extraction can be taken. For Part 2 and 3, excisional/incisional biopsies preferred from non-lymph node lesion and tumor tissue samples will be centrally assessed for sufficient tumor content (≥ 100 tumor cells/4-micon section); subjects with samples that have insufficient tumor content will require re-biopsy prior to treatment. In Part 4, pre-treatment and on-treatment biopsies are optional; although strongly recommended if clinically safe. For Parts 1-4, archival tissue (FFPE block or a minimum of 10 unstained slides) should be obtained if available. See Section 5.6 for detail.
Blood Samples for Biomarkers	X		See Table 5.5A or Table 5.5B and Laboratory Manual for more details

Table 5.1A: CA209038 Screening Procedural Outline			
Procedure	Screening Visit	Visit 1 Day -3 to Day 1	Notes
Disease Assessments	X		CT chest, CT or MRI abdomen and pelvis, as well as MRI of brain should be performed if not performed within 28 days of anticipated drug administration.
Safety Assessments			
Assessment of Signs and Symptoms	X		Within 2 weeks prior to treatment; Record all medications taken within the prior 28 days as per Section 3.4

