Study Day	Time (Event)	Time (Relative to Start of Infusion) Hours:Min	SNP& HLA/ KIR typing	Tumor Ag specific T-cells with a CBC and differential	MDSCs	PB Gene Expression Profiling	PBMC Flow Cytometry with a CBC and differential	Soluble Factors (Serum)	Anti-Tumor Antibodies	PBMC Functional Assays with a CBC and differential	Tumor Biopsy
Week 3 Day 1	0 (predose)	00:00				X	X ^a	X		X ^a	
Week 4 Day 1	0 (predose)					X	X ^a	X		X ^a	X (+7 days after 2nd dose) ^{c,e}
Week 5 Day 1	0 (predose)	00:00		X ^a		X	X ^a	X		X ^a	
Week 7 Day 1	0 (predose)	00:00			X	X	X ^a	X	X	X ^a	
Week 13 Day 1	0 (predose)	00:00		X ^a			X ^a		X	X ^a	
Follow-up Visit 1 (40-60 days after last treatment)											X - obtain upon progression ^f
Follow-up Visit 2 (101-120 days after last treatment)											X - obtain upon progression ^f

Table 5.5B: CA209038 Pharmacodynamic and Biomarker Sampling Schedule (Parts 2, 3 and 4, Arms A, B, D and E)

Study Day	Time (Event)	Time (Relative to Start of Infusion) Hours:Min	SNP& HLA/ KIR typing	Tumor Ag specific T-cells with a CBC and differential	MDSCs	PB Gene Expression Profiling	PBMC Flow Cytometry with a CBC and differential	Soluble Factors (Serum)	Anti-Tumor Antibodies	PBMC Functional Assays with a CBC and differential	Tumor Biopsy
Upon occurrence of \geq Grade 3/4 drug-related AE								X			
Local surgery of isolated symptomatic lesions (see Section 3.4.1)											X ^f
Re-treatment after interrupted active treatment											X ^f

^a CBCs required will be done locally and not by central lab

^b Must contain sufficient tumor content (\geq 100 tumor cells in a 4 micron section) upon central pathology assessment;

^c Biopsy is strongly encouraged but not mandatory in Part 4

^d On-treatment biopsy window for Part 2, group 1 biopsy is Week 2, Day 1+7 days; potential on-treatment biopsy window for Parts 3 and 4, if determined to be optimal biopsy window.

^e On-treatment biopsy window for Part 2, group 2 is Week 4, Day 1+7 days; potential on-treatment biopsy window for Parts 3 and 4, if determined to be optimal biopsy window.

^f Biopsy is strongly encouraged but not mandatory. May be done at either Follow-up visit 1 or Follow-up visit 2

Table 5.5C: PK and ADA Sampling Schedule - Part 2 Arm A

Study Day	Time (Event)	Time (Relative to Start of Nivolumab Infusion) Hours Min ^a	PK Serum Sample Nivolumab	Immuogenicity Sample Nivolumab	PK Serum Sample Ipilimumab	Immunogenicity Sample Ipilimumab
Week 1 Day 1	0 (predose)	00:00	X	X	X	X

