In Part 4, approximately 20 anti-CTLA4 therapy-naive patients with brain metastases will be randomized 1:1 and treated with one of the following:

- Arm D: nivolumab 1 mg/kg IV combined with ipilimumab 3 mg/kg IV Q3W for 4 doses then nivolumab 3 mg/kg IV Q2W
- Arm E: nivolumab 3 mg/kg IV Q2W

In Parts 2, 3 and 4 of this study, patients will also go through a screening period of no longer than 28 days. In Parts 2 and 3, pre-treatment samples will be centrally assessed for tumor content and subjects who have samples with insufficient tumor content (< 100 tumor cells in a 4 micron tissue section) will require re-biopsy or will not be treated. In Part 4, tumor biopsy collection is optional, but strongly encouraged if clinically safe. Eligible subjects will then start the treatment period for a duration of two years of therapy. Subjects randomized to Arm C in Part 3 of this study prior to the closure of this Arm have the option to receive nivolumab monotherapy upon consultation with the medical monitor.

Response assessments will be performed approximately every 8 weeks (may differ by several weeks depending on treatment arm). The response assessment must be completed before the first dose in the next treatment visit.

At the completion of 2 years of therapy, those subjects who are benefiting and still meet study criteria may continue after discussion and agreement between the investigator and Medical Monitor and will enter the Extension Period. Treatment in the Extension Phase will continue until progression of disease or unacceptable toxicity.

Subsequent to a duration of 2 years of active treatment or following the last dose of treatment in the Extension Period, each patient will continue follow-up consisting of office visits, lab work and tumor assessments for a maximum period of up to 100 days; follow-up office visits 1 and 2 (40-60 days and 101-120 days after the stop of study therapy). Completion of subsequent follow-up office visits will depend on the status of the subject at the end of the treatment period.

Patients with confirmed disease progression will complete follow-up office visits 1 and 2 and will then continue follow-up by telephone assessment every 3 months for the remainder of time left to complete 2 years from the first dose of treatment.

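### Inclusion criterion 2(e)(iv) sets 100 tumour cells as an upper limit for a sufficient biopsy, where every other visible statement of the rule makes it a lower limit

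*Protocol*

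**What the plan says.** The tumour-content rule for pre-treatment biopsies in Parts 2 and 3 appears six times in the visible text.

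- **Protocol Section 3.3.1, criterion 2(e)(iv):** "pre-treatment tumor samples must contain sufficient tumor content (≤ 100 tumor cells/4-micron tissue section) upon central assessment". The sentence that follows gives the consequence: "If sample contains insufficient tumor content, a re-biopsy will be required to obtain a sample with sufficient tumor content prior to treatment".
- **Protocol Synopsis (Study Design) and Section 3.1**, in the same words: "samples with insufficient tumor content (≤ 100 tumor cells in a 4 micron tissue section) will require re-biopsy or will not be treated".
- **Protocol Table 5.1A** (tumor tissue row): "centrally assessed for sufficient tumor content (≥ 100 tumor cells/4-micon section".
- **Protocol Table 5.5B, footnote b**, which sets the requirement at or above "100 tumor cells in a 4 micron section) upon central pathology assessment".
- **SAP Section 2.1:** "insufficient tumor content (< 100 tumor cells in a 4 micron tissue section) will require re-biopsy or will not be treated".

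On the force of the eligibility criteria, Protocol Section 3.3 says: "It is imperative that subjects fully meet all eligibility criteria. No exceptions will be granted".

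**The concern.** Criterion 2(e)(iv) attaches to the word *sufficient* the same inequality that the Synopsis and Section 3.1 attach to *insufficient*. Followed as written, it accepts sparse tissue and sends tumour-rich tissue for a repeat invasive procedure before treatment.

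The place of the error gives it weight. It is in the eligibility criterion itself, not in a summary. A site that follows the sensible reading departs from the literal criterion, and Section 9.1.1 bars deviations without ethics approval except to remove an immediate hazard. A site that follows the criterion contradicts the design section and the screening table.

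The rule also screens the baseline tissue. Tumour T-cell infiltration is among the primary endpoints (Protocol Section 8.3.1; SAP Table 4.1-1), and Part 2 chooses the on-treatment biopsy window by comparison with the pre-treatment biopsy. SAP Section 7.2.3 lists the programmable eligibility deviations, and 2(e)(iv) is not among them. A misapplied rule might still appear in the separate listings of non-programmable deviations, but no programmed check is named.

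**Working it through.** No power or precision figure depends on this rule. The check is to apply each statement literally to samples on either side of the threshold and at it.

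**Step 1: the rules as written** (n = tumour cells per 4-micron section)

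- Criterion 2(e)(iv): sufficient if n ≤ 100.
- Synopsis and Section 3.1: insufficient if n ≤ 100, so sufficient if n > 100.
- Table 5.1A and Table 5.5B footnote b: sufficient if n ≥ 100.
- SAP Section 2.1: insufficient if n < 100, so sufficient if n ≥ 100.

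**Step 2: classification**

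| Statement | n = 99 | n = 100 | n = 101 |
|---|---|---|---|
| Criterion 2(e)(iv) | sufficient | sufficient | insufficient: re-biopsy |
| Synopsis; Section 3.1 | insufficient | insufficient | sufficient |
| Table 5.1A; Table 5.5B fn b; SAP 2.1 | insufficient | sufficient | sufficient |

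**Step 3: reading the table**

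- Against the Synopsis and Section 3.1, criterion 2(e)(iv) gives the opposite answer at every count.
- Against Table 5.1A, Table 5.5B footnote b and SAP 2.1, it gives the opposite answer at every count except exactly 100.
- No sample satisfies all six statements. Below 100 it fails five of them, above 100 it fails 2(e)(iv), and at exactly 100 it fails the Synopsis and Section 3.1.
- Correcting 2(e)(iv) alone would leave the disagreement at exactly 100.

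**Step 4: how many subjects the rule touches**

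The plan treats about 20 subjects in Part 2 and 30 in Part 3, so 20 + 30 = 50. The rule acts at screening, so the relevant number is larger. The Synopsis gives the study-wide figure: "approximately 200 subjects will be screened (25% screen fail rate". This is reproduced by 150 / (1 − 0.25) = 200. The documents give no rate for Parts 2 and 3 alone. Assuming the same 25%, 50 / 0.75 ≈ 67 subjects would be screened. For assumed rates of 10% and 40% the figures are 50 / 0.90 ≈ 56 and 50 / 0.60 ≈ 83. These are numbers exposed to the rule, not numbers misclassified. The documents give no distribution of cell counts from which misclassification could be estimated.

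**The case against.** The strongest reply is that this is a one-symbol slip that explains itself. A requirement for sufficient content makes no sense as a ceiling, and five other statements give the direction. Assessment is central, so individual sites do not each interpret the inequality. SAP Section 7.8.2 separately requires at least 100 evaluable tumour cells for PD-L1 expression. That is an assay rule rather than the biopsy rule, but it points the same way and keeps low-content samples out of that analysis. SAP Section 6.3 limits each marker's dataset to subjects with an evaluable measurement, and Protocol Section 4.2 replaces subjects in these parts who lack paired biopsies. On this view a wording correction is enough.

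Much of this stands. The intended direction is recoverable, other provisions limit the effect on the analyses, and no harm is documented. It does not remove the conflict. A central assessor still needs one stated rule, and the documents give three. The later provisions act after the biopsy decision, so they do not settle who has a repeat procedure or who may be treated.

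Two limits on the evidence should be noted. Table 5.1A refers to Section 5.6 for detail, and that section is not in the public text, so the count of six covers visible statements only. A symbol misread from the PDF cannot be fully excluded. However, both inequality signs are rendered elsewhere in the same criteria, and the split at exactly 100 among the other five statements would remain in any case.

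**Conclusion.** The concern holds. One of six visible statements has its direction reversed, and it is the binding one. The other five agree on direction but divide two to three at exactly 100 cells. The consequence is contradictory instructions on entry and repeat biopsy for Parts 2 and 3. Whether any subject was actually handled wrongly depends on the rule the central assessor used, which the documents do not state. The correction should be made despite the recoverable intent, because a no-exceptions entry criterion that governs an invasive procedure should not state the reverse of the design text.

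**What to change.** 1. Reverse the inequality in criterion 2(e)(iv) so that 100 cells is a lower limit.
2. Reconcile all six statements (Synopsis, Section 3.1, criterion 2(e)(iv), Table 5.1A, Table 5.5B footnote b, SAP Section 2.1) to one boundary. The sponsor should decide how exactly 100 cells is classified. The two tables and the SAP already agree with one another; the Synopsis and Section 3.1 are the two that differ from them at that count.
3. Check the unpublished Section 5.6 for a further statement of the rule and align it if there is one.
4. Obtain confirmation of the rule the central assessor has been applying.

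The cost is a wording correction in a protocol amendment, with SAP Section 2.1 aligned if the chosen boundary differs from it, and one query to the central assessor. No extra subjects, procedures or analyses are needed.
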